ASCO Survey on COVID-19 in Oncology (ASCO) Registry

Study Schema - 10.6.2020

Rationale

The COVID-19 Pandemic presents a unique opportunity to capture information on how a disease outbreak affects delivery of high-quality cancer care. ASCO is providing the means for the oncology community to rapidly submit data that will inform both current cancer care and provide information to help guide decision-making for future disease outbreaks. While other entities have launched COVID-19 cancer registries, ASCO has extensive relationships with the entire cancer care community, particularly private practices that may be caring for the majority of cancer patients with COVID-19. ASCO's registry collects information about patients undergoing treatment for cancer and with confirmed COVID-19 infection based on a positive test. Unlike other registries, ASCO's registry collects follow-up information on both COVID-19 disease and cancer outcomes at 30-day intervals for the first 90 days and 90-day intervals thereafter up to one year after COVID-19 diagnosis.

Project Objectives:

Capture and describe cancer and COVID-19 status at COVID-19 diagnosis, and cancer and COVID-19 outcomes of patients with cancer and COVID-19 from participating cancer practices/institutions. Data collected will include treatment approaches, cancer status, changes to cancer treatment plans in patients with confirmed SARS-CoV-2 infection, status of COVID-19 infection (e.g., severity of symptoms, need for ventilator, hospitalization, etc.) and cancer (e.g., cancer progression, treatment-related changes/modifications, etc.).

Project Deliverables:

- Periodic Reports on Patient Population, Estimates of Disease Severity, Treatment Modifications, and Clinical Outcomes Among Patients – for participating sites and publicly accessible on ASCO websites for the oncology community
- Manuscript(s) for Submission to Peer-Reviewed Journals

Research Objectives:

Objective 1: Describe the distribution of symptoms and severity of COVID-19 among patients with cancer (on active treatment or on adjuvant treatment within 12 months after surgical resection) who have confirmed infection of SARS-CoV-2

- **Objective 1.1:** Describe distribution of symptoms and severity of COVID-19 stratified according to demographic characteristics, including age, cancer type, cancer extent, race, ethnicity, geography, type of therapy received, smoking status, comorbidities, etc.

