ASCO's Center for Research and Analytics (CENTRA) will periodically create reports to share with participating practices and the general cancer community, and submit manuscripts for publication. Reports will summarize overall and stratified by patient characteristics, such as disease sites and stage, age and comorbidities. Reports or publications will also include cancer treatment delay and discontinuation of cancer treatments including surgery, radiation and drug-based therapies, due to the patient's COVID-19 disease and to other factors, with stratification by other variables as described above. Changes in practices' patterns of care, staffing, resources, and interactions with patients will also be evaluated and summarized.

As there is no hypothesis testing planned, there is no required sample size and providing repeated reports, with cumulative information, will not affect validity of results. Confidence intervals will be provided where appropriate to demonstrate precision of estimates.

IRB Review

ASCO received approval from the Western Institutional Review Board (WIRB):

"We determined this study is exempt from IRB review because it does not meet the definition of human subject as defined in 45 CFR 46.102. Specifically this study will [sic] deidentified data in the form of limited data sets from the participating clinics and institutions and you will enter into Data Use Agreements, and you will not otherwise interact with the patients."

The WIRB letter is available on the ASCO Registry website. ASCO encourages practices to rely on the WIRB review. If local IRB approval is necessary, the review must be completed before the practice can execute the data use agreement (DUA) with ASCO.

Practice Expectations (Refer also to study calendar in Appendix.)

- Review study schema, data collection elements, and WIRB determination.
- Complete practice contact information (link available at the ASCO Registry website) and download the DUA. In the interest of prompt data reporting, ASCO will only entertain DUA revisions related to the local site contact information.
- Contact [contact] to express interest in participation and execute DUA with ASCO.
- Access web address provided by ASCO for data entry and select practice name from the dropdown list of practices that have executed a DUA.

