- Complete initial and follow-up data entry forms. Follow-up data includes information on COVID-19 and cancer treatment and outcomes. Ideally, data entry will be done routinely. ASCO requests case updates at 30-, 60-, 90-, 180-, 270-, and 360-day intervals, unless a patient has left the practice or died. Where necessary, practices should attempt to obtain information from inpatient hospitalizations.
 - Data includes:
 - Limited patient identifiable data, including home zip code, practice zip code, and date of birth
 - Demographics (e.g., gender, race, ethnicity, type of cancer, and comorbidities)
 - COVID-19 status (e.g. symptoms, treatments, and outcomes)
 - Cancer status (e.g., treatment plans, any changes to treatment plans, and response to treatments)
 - ASCO encourages practices to create a local standard operating procedure (SOP) to arrange systematic data entry. Retrospective data could be retrieved from the EHR using the new ICD-10-CM diagnosis code U07.1 (created by the Centers for Disease Control and Prevention (CDC) on March 18, 2020). Previous ICD-10-CM codes were 1)
 Coronavirus, as cause of disease classified elsewhere B97.29, 2) Coronavirus NEC B34.2, and 3) SARS-associated coronavirus J12.81. The coding system for laboratory and clinical test results (LOINC) has also established several codes for tests for the COVID-19 virus: SARS Coronavirus 2.
 - Practices may have to contact the hospital for information regarding an inpatient admission.
- ASCO provides participating sites with a practice-based stipend in the first 30 days following contract execution and case-based stipends after the first 30-day update to help cover the costs of entering registry data.

Participating practices are listed on the ASCO Registry webpage. Practices may withdraw from the registry at any time.

Please contact [contact] for additional information or questions.

The ASCO Registry is supported by Conquer Cancer's **COVID Impacts Cancer Fund**.

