Appendix – Study Calendar and Timelines

Study Calendar for Patients in ASCO Survey on COVID-19 in Oncology Registry

[figure not shown]
This schedule is intended to ensure consistent reporting across practices. It is important for practices to follow the schedule as close as possible because deviations may impact the quality of data in the registry and accuracy of inferences. However, ASCO acknowledges that adjustments may need to be made for some practices.

Phase	Initial Entry		Short term Follow-up		Long-term Follow-up
	Initial at time of COVID-19 diagnosis ¹	1 month after COVID-19 diagnosis	2 months after COVID-19 diagnosis	3 months after COVID-19 diagnosis	6, 9 and 12 months after COVID-19 diagnosis
Initial Entry: At time of COVID- 19 diagnosis					
Initial Clinical and Demographic Information	•				
COVID-19 Diagnosis Symptoms, and Treatment	•				
Cancer Diagnosis, Status, and Treatment	•				
Short Term Follow-up					
COVID-19 Status Update		•	•	•	
Cancer Status Update		•	•	•	
Long Term Follow-up					
COVID-19 Long-term Update					•
Cancer Long-term Update					•

¹ If patient is deceased at the time of initial form submission or leaves practice prior to 30 days, a practice should complete a patient update form at any time and receive payment for the case in that month.

ASCO Registry

Registry Schedule for Participating Practices

¹Patient COVID-19 and cancer status updates should be entered every 30 days for first 90 days and every 90 days thereafter, for at least 12 months, closure of registry, or death/patient leaves practice (whichever occurs first).

³Practice status updates may be requested periodically.

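### Is the protocol wrong to say that repeated cumulative reports leave validity intact, when early outcome proportions could be biased by form timing?

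*Protocol*

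**What the plan says.** Statistical Considerations and Reporting plans no hypothesis test. From this it draws two consequences: no sample size is required, and "providing repeated reports, with cumulative information, will not affect validity of results". Confidence intervals are promised where appropriate, to show precision.

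The periodic reports are listed under Project Deliverables and will be public. They cover "Estimates of Disease Severity, Treatment Modifications, and Clinical Outcomes Among Patients".

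The timing of forms is set in two places.

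- **Practice Expectations:** "ASCO requests case updates at 30-, 60-, 90-, 180-, 270-, and 360-day intervals, unless a patient has left the practice or died". On entry itself it says "Ideally, data entry will be done routinely", and it adds that "Retrospective data could be retrieved from the EHR".
- **Appendix – Study Calendar and Timelines:** initial entry is placed at the time of COVID-19 diagnosis. Footnote 1 of the patient calendar makes an exception: "If patient is deceased at the time of initial form submission or leaves practice prior to 30 days", then "a practice should complete a patient update form at any time and receive payment for the case in that month". The text introducing the calendar warns that "deviations may impact the quality of data in the registry and accuracy of inferences".

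The protocol gives no denominator for any outcome proportion, no report dates, no expected mortality and no accrual rate.

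**The concern.** The only reason offered for validity is the absence of testing. That disposes of type I error from repeated looks, but validity normally also covers whether a proportion estimates what it appears to estimate. The protocol's own form rules suggest two ways in which an early cumulative proportion could be off.

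- **Form timing.** Most first updates fall due at day 30, but a patient already dead when the first form is submitted may have an update at any time. If first forms come in some days late, early deaths join the updated cases before survivors diagnosed on the same dates. The death proportion among updated cases is then too high.
- **Incomplete follow-up.** At any cut, recently diagnosed patients have no day-30 status. If they count in the denominator, the proportion is too low.

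If either were built into the plan, public figures for death or recovery could drift from one report to the next for reasons unrelated to the disease. The planned intervals would not reveal it, because they describe precision and not bias.

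**Working it through.** **1. What the sentence asserts.** Its subject is the issuing of repeated cumulative reports, and its premise is that nothing is tested. The question is therefore whether issuing several reports changes the validity of any one of them. It does not say that each report is free of ascertainment bias.

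**2. Does repetition enter the bias?** Let T be the day of the data cut, m the true 30-day mortality and L the lag from diagnosis to first form. Reading footnote 1 literally, a patient dead by L has an update at L, and everyone else has one at max(30, L). Two candidate proportions are:

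- updated cases: deaths with an update by T / cases with an update by T;
- all entered: deaths with an update by T / cases entered by T.

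Both depend only on T, m, L, the death times and accrual. The number of earlier reports appears in neither. One report at T and the tenth report at T give the same figure.

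**3. Size of the effects.** The protocol has no figure to reproduce, so every input here is assumed: m = 15%, death times truncated exponential (scale 12 days, cut at 30), uniform accrual over [0, T], and L exponential with mean 7, 14 or 30 days.

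| Cut T (days) | Updated cases | All entered |
|---|---|---|
| 60 | 17.8–18.2% | 10.6–12.5% |
| 90 | 16.3–16.6% | 12.2–13.6% |
| 180 | 15.5–15.6% | 13.6–14.4% |
| 365 | 15.2–15.3% | 14.4–14.7% |

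A Monte Carlo run with 3,000,000 patients per scenario agrees within about 0.1 point. The direction depends on a denominator that the protocol does not choose. Restricting to patients diagnosed at least 30 days before the cut returns 15.0% at every T.

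**4. When the effects vanish.**

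- *On-time entry (L = 0), as the calendar asks.* Nobody is dead at first submission, so all updates fall at day 30. Updated cases give m = 15.0% at every cut. All entered gives m(T − 30)/T, which is 0.15 × 30/60 = 7.5% at day 60 and 0.15 × 150/180 = 12.5% at day 180. That shortfall is ordinary immature follow-up and owes nothing to footnote 1.
- *Every case entered at or after day 30.* Now max(30, L) = L, so the dead and the living have the same form date, which is also the entry date. Both proportions equal m: 15.0% at cuts of 60, 90, 180 and 365 days with fixed lags of 30 or 45 days.

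Retrospective entry can therefore remove both effects. The upward effect needs first forms submitted after diagnosis but before day 30. An exponential lag with mean 30 days still shows it because 1 − exp(−30/30) = 63% of first forms come before day 30.

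**5. Does the protocol claim immunity from timing effects?** No. Under the calendar's own timing the upward effect is nil, so it needs initial entry later than scheduled. The appendix says that departures from the schedule may affect data quality and the accuracy of inferences.

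**The case for a change.** The strongest case for the concern is that the sentence carries no qualification. A lay reader of a public report may take it as assurance that early figures can be trusted. Footnote 1 is a permitted route, and Practice Expectations permits retrospective retrieval, so one can argue that the appendix's warning about deviations does not reach them. If every death were reported at once, with uniform death times, prospective entry and survivors reported at day 30, the proportion among updated cases at day 60 would be 0.15 × 0.75 / (0.15 × 0.75 + 0.85 × 0.50) = 20.9%. Accrual growing 1 to 2% a day would keep the literal-footnote figure at 16.1 to 17.5% at day 180. Further, Objectives 1.2, 2.1 and 2.2 seek independent associations. The chance that at least one of several cumulative 95% intervals misses the truth is 14.1% over 5 looks and 19.3% over 10.

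Part of this stands. An outcome proportion from an immature cut can mislead, and whoever analyses the registry should fix a follow-up window and show how many patients have unknown status. The rest does not make the sentence wrong. The 20.9% assumes immediate reporting of all deaths, whereas footnote 1 speaks only of patients dead at initial submission. The accrual growth is assumed too. Each interval, taken alone, keeps its nominal coverage, and the protocol attaches no test or decision to a run of them. Narrower wording would be tidier, but it would alter no estimate.

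**Conclusion.** The concern does not hold. Read with its premise, the sentence says that repeated reporting raises no validity problem when nothing is tested, and that is correct for what it addresses. The biases come from an immature data cut combined with a particular denominator, and the protocol commits to no such denominator. Defining the window, the entry allowance and the handling of unknown status is detail commonly left to a statistical analysis plan. None is at hand here, so its absence from the protocol is not an error.

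On the assumed inputs with constant accrual, the form-timing effect is about +3 points at day 60, +0.5 to +0.6 at day 180 and +0.2 to +0.3 at day 365. It is nil with on-time entry or when every case is entered at or after day 30. These sizes rest wholly on assumed mortality, death timing, entry lag and accrual. The logical point, that the number of reports does not enter the bias, rests on none of them.

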- **Objective 1.2:** Identify characteristics independently associated with severity of COVID-19 in cancer patients.

Objective 2: Examine SARS-CoV-2 viral infection outcomes (ongoing, recovery, hospitalized, not in ICU; hospitalized in ICU; placed on ventilator; death due to COVID-19 disease complications) and

cancer outcomes (stable, response to treatment, progression, delayed treatment, treatment discontinued, and death)

- Objective 2.1: Stratify patients with SARS-CoV-2 viral infection according to characteristics
 described in Objective 1.1 to examine whether any of the characteristics are independently
 associated with COVID-19 and/or cancer outcomes
- Objective 2.2: Examine the relationship between SARS-CoV-2 viral infection outcomes and cancer outcomes and whether SARS-CoV-2 viral infection outcomes are independently associated with cancer outcomes

Objective 3: To describe effects of the COVID-19 pandemic on cancer practices in the U.S., including changes in staffing and resource availability, prioritizations for patient care, and modification of interactions between care providers and patients (including use of telemedicine)

Eligibility Criteria:

The registry will collect data about patients with a cancer diagnosis who have a confirmed SARS-CoV-2 infection and are being treated at participating cancer practices/institutions within the United States.

Patients in one of the four categories are eligible:

- 1. Patients with a new cancer diagnosis and in the process of cancer staging and/or receipt of initial cancer therapy
- 2. Patients with clinically evident cancer receiving anti-cancer treatment,
- 3. Patients who are disease free, but receiving any type of adjuvant therapy within 1 year following surgical resection (including hormonal treatments), and
- 4. Patients with clinically evident cancer receiving supportive care only.

Statistical Considerations and Reporting

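### The protocol sets no rule to enter all or consecutive eligible patients and names no completeness check, so COVID-19 severity proportions may be biased in either direction without the planned confidence intervals showing it

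*Protocol*

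**What the plan says.** Objective 1 in the Protocol's Research Objectives is to "Describe the distribution of symptoms and severity of COVID-19 among patients with cancer". Objective 2 adds outcomes such as hospitalization, intensive care, ventilation and death.

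The Eligibility Criteria section opens as follows: "The registry will collect data about patients with a cancer diagnosis who have a confirmed SARS-CoV-2 infection and are being treated at participating cancer practices/institutions". Only sites in the United States take part. Four cancer-status categories follow. The section does not say all or consecutive patients, and it sets no date from which a practice must start to count.

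Practice Expectations asks for initial and follow-up forms and comments: "Ideally, data entry will be done routinely". It continues: "ASCO encourages practices to create a local standard operating procedure (SOP) to arrange systematic data entry". On case finding it offers an option: "Retrospective data could be retrieved from the EHR using the new ICD-10-CM diagnosis code U07.1". Practices receive a practice stipend and "case-based stipends after the first 30-day update to help cover the costs of entering registry data"; neither is linked to the share of eligible patients entered.

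The Appendix places the initial form at COVID-19 diagnosis and asks practices to keep close to the schedule. Footnote 1 of the patient calendar covers a patient who has already died when the initial form is submitted, or who leaves before 30 days: "a practice should complete a patient update form at any time and receive payment for the case in that month".

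Statistical Considerations and Reporting states: "As there is no hypothesis testing planned, there is no required sample size". It plans confidence intervals to show precision and does not discuss which patients are entered.

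**The concern.** A distribution of severity is a set of proportions, and each depends on who is in the denominator. If patients with severe and mild infection have different chances of being entered, every proportion moves, even when each form is filled in perfectly.

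The protocol leaves room for this. Nothing obliges a practice to enter every eligible patient or to take them in sequence, and a case may be entered when its outcome is already known. The Appendix warns that departures from the reporting schedule can harm the accuracy of inferences, but gives no matching warning about which patients enter.

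The results go into public reports and manuscripts. A confidence interval around a selectively built proportion narrows as cases accumulate, but it stays centred on the wrong value. An analysis plan could not repair this later, because a count of eligible patients has to be gathered at the practices.

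**Working it through.** **No figure to reproduce.** The protocol gives no severity rate, sample size or expected completeness. Everything below is illustrative, with assumed inputs.

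**Inputs.** *p* is the true share of severe cases among eligible patients (assumed, 10% to 40%). *k* is the chance of entry for a severe case divided by that for any other case (assumed, 0.5 to 3; 1 means no selection).

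**Formula.** Observed share = *pk* / (*pk* + 1 − *p*).

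**Worked case, *p* = 30%.**
- *k* = 0.5: 0.15 / (0.15 + 0.70) = 17.6%
- *k* = 1: 0.30 / (0.30 + 0.70) = 30.0%
- *k* = 3: 0.90 / (0.90 + 0.70) = 0.5625, shown as 56.2%

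**Full grid (observed share, %).**

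| True share | k = 0.5 | k = 0.67 | k = 1 | k = 1.5 | k = 2 | k = 3 |
|---|---|---|---|---|---|---|
| 10% | 5.3 | 6.9 | 10.0 | 14.3 | 18.2 | 25.0 |
| 20% | 11.1 | 14.3 | 20.0 | 27.3 | 33.3 | 42.9 |
| 30% | 17.6 | 22.3 | 30.0 | 39.1 | 46.2 | 56.2 |
| 40% | 25.0 | 30.9 | 40.0 | 50.0 | 57.1 | 66.7 |

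**Milder selection also matters.** With a true 30% and entry chances of 0.9 for hospitalized and 0.7 for other patients, the observed share is 0.27 / (0.27 + 0.49) = 35.5%.

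**What the confidence interval shows.** Take *p* = 20% and *k* = 2, so the observed share is 0.40 / 1.20 = 33.3%. The 95% half-width is 1.96 × √(0.333 × 0.667 / *n*):
- *n* = 500: 29.2% to 37.5%
- *n* = 1000: 30.4% to 36.3%
- *n* = 2000: 31.3% to 35.4%

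Each interval excludes the true 20%, and a larger registry only tightens it around the biased value.

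**Direction.** The document points both ways. Severe cases may be more prominent to a practice, which is an assumption. Against that, Practice Expectations notes that practices may need to approach a hospital for admission details, which could make inpatient cases harder to enter. So *k* below 1 is as admissible as *k* above 1.

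**The case against.** **The sentence on routine entry is not about completeness.** It stands between the request to complete forms and the 30- to 360-day update schedule. A reader might infer that entering every eligible case is declared a mere ideal; the protocol does not say so. This objection stands. The point rests instead on the missing all-or-consecutive rule and the merely encouraged local procedure.

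**A count may exist elsewhere.** Practices are told to review a separate list of data elements, Objective 3 collects practice-level information, and practice status updates may be requested. The content of these is not shown, and the practice schedule is incomplete in the text available. It therefore cannot be said that no count is collected, only that none is named. This stands.

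**Selection could be probed.** Severity mix could be compared between practices, or the code search could be run to count cases. A reader might infer that the bias is undetectable, which is too strong. What is true is that no such check is described.

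**Retrospective retrieval is not itself a fault.** A code search can find cases more systematically than memory. The Appendix also asks for initial entry at diagnosis, and payment for early deaths removes one reason to omit them. This is fair, but the search is optional, and the payment rule does nothing for mild cases left out.

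**This is a voluntary, descriptive registry.** Incomplete capture is a familiar limit of such designs, and there is no hypothesis test to invalidate. That limits the severity of the point. It does not remove it, because the proportions are the main product.

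**Conclusion.** The concern holds in a limited form. Read as written, the protocol permits entry that depends on severity or on a known outcome, and it names neither an eligible-patient count nor a completeness check. The Objective 1 and 2 proportions could be biased up or down, and the planned confidence intervals would not show it.

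For an assumed true severe share of 30%, entry ratios of 0.5 to 3 give an observed 17.6% to 56.2%. These ratios are assumptions that show sensitivity; they do not estimate the bias actually present. A reader might infer that severity is necessarily overstated, but nothing in the protocol establishes that direction.

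The registry remains useful without the change. Its headline proportions would simply be hard to interpret as describing all eligible patients at the participating practices. The illustration concerns proportions only; the effect on the associations in Objectives 1.2 and 2.1 was not assessed.

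**What to change.** 1. **Entry rule.** In Eligibility Criteria and Practice Expectations, state that each practice enters all eligible patients with a positive test from a practice-specific start date. If it cannot, it enters consecutive patients up to a stated cap.
2. **Timing flag.** Mark each case as entered before or after its day-30 outcome was known, derived from the diagnosis date and the date of initial entry (assuming the web form records the latter). Deriving it from dates keeps patients who die early from being reclassified merely because they died. Repeat the main severity tables in prospectively entered cases, as a sensitivity comparison and not a correction.
3. **Completeness, where feasible.** Ask each practice periodically for the number of patients found by code or laboratory search and confirmed eligible. Report completeness and show severity by completeness level. A fixed cut-off such as 80% has no basis in the protocol and is best avoided.
4. **Limitation.** State in reports that practices select themselves into the registry, which none of these steps addresses.

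Items 1 and 2 are cheap: a wording change and a derived variable. Item 3 costs more, because a COVID-19 code search does not establish which of the four cancer-status categories a patient meets, so some chart review of the hits is needed. The consecutive-to-a-cap option limits the burden.
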